**Table 9-1 : Categorized dose of vinflunine**

Dose category in mg/m 	Dose of vinflunine in mg/m 
>320	] 335 – • ]
320	] 300 – 335 ]
280	] 265 - 300 ]
250	] 237.5 - 265 ]
225	] 212.5- 237.5 ]
< 225	] 0 - 212.5 ]

The following categories of methotrexate doses will be used:

**Table 9-2 : Categorized dose of methotrexate**

Dose category in mg/m 	Dose of methotrexate in mg/m 
>40	] 45 - • [
40	] 35 - 45 ]
30	] 25 - 35 ]
20	] 15 - 25 ]
<20	] 0 - 15 ]

The dose intensity (mg/m^2/wk) and relative dose intensity (%) will be calculated per patient and per cycle for each treatment drug. Cumulative dose of vinflunine or methotrexate (mg/m^2) will also be provided per patient. Descriptive statistics such as median and range will be provided.

Moreover, for both treatment arms, relative dose intensity will be categorised (< 50%, [50% -70%[, [70% - 90%[, [90% - 110%[, ≥ 110%) per patient and per cycle.

### 9.2.1. Dose intensity per cycle

Actual dose intensity per cycle will be defined as follows :

$$DI \text{ at cycle } i = \frac{\text{Actual dose received at cycle } i}{\text{Actual duration of cycle } i \text{ (wk)}} = \frac{\text{Actual dose received at cycle } i}{[(\text{Course date at cycle } i + 1) - (\text{Course date at cycle } i)]}$$

The cycle duration at cycle n will be equal to the time elapsed between the day 1 administration date of cycle n and the day 1 administration date of cycle n+1. The duration of the last cycle will be estimated to be 3 weeks.

### 9.2.2. Relative dose intensity per cycle

Relative dose intensity (%) at cycle n° i will be the ratio of the actual dose intensity (mg/m^2/wk) at cycle i to the planned dose intensity (mg/m^2/wk) that is to say :

$$RDI \text{ at cycle } i = \left( \frac{DI \text{ at cycle } i}{PDI} \right) \cdot 100 = \left( \frac{\text{Actual dose intensity at cycle } i}{\text{Planned dose intensity}} \right) \cdot 100$$

where :

$$PDI \text{ at cycle } i = \frac{\text{Planned dose}}{\text{Theoretical duration of cycle } i \text{ (wk)}}$$

The theoretical cycle duration is 3 weeks. The planned dose for each drug is defined as follow:

Table 9-3: Planned dose intensity in mg/m^2/wk of vinflunine

Planned Dose (mg/m  ) per cycle	Cycle duration (wk)	P.D.I (mg/m  /wk)
280	3	93.33

Table 9-4: Planned dose intensity in mg/m^2/wk of methotrexate

Treatment arm	Planned Dose (mg/m  ) per cycle	Cycle duration (wk)	P.D.I (mg/m  /wk)
Arm A	60	3	20
Arm B	120	3	40

### 9.2.3. Dose intensity per patient

Actual dose intensity per patient will be defined as follows:

$$DI = \frac{\text{Cumulative dose}}{\text{Treatment duration (wk)}} = \frac{\sum_{i=1}^n \text{dose}_i}{\sum_{i=1}^n \text{duration}_i}$$

where:

- dosei = actual dose received (mg/m^2) at cycle *i*,
- durationi = actual duration (wks) of cycle *i*,
- n = total number of cycle(s) per patient.

### 9.2.4. Relative dose intensity per patient

Relative dose intensity (%) will be the ratio of the actual dose intensity (mg/m^2/wk) to the planned dose intensity (mg/m^2/wk) that is to say :

$$RDI = \left( \frac{DI}{PDI} \right) \cdot 100 = \left( \frac{\text{Actual dose intensity}}{\text{Planned dose intensity}} \right) \cdot 100$$

PDI is defined for each arm in the section 9.2.2.

### 9.2.5. Dose reductions

Dose reductions are allowed by the study protocol. The number of patients and cycles with a dose reduction in each arm will be presented as well as the reasons.

#### 9.2.5.1. Vinflunine dose reduction (Arm A)

- Number of patients with at least one dose of vinflunine reduced at day 1.
- Number of cycles with a dose of vinflunine reduced at day 1.
- Reasons for vinflunine dose reduction:

Reason for dose reduction of vinflunine	Dose reduction as per protocol				N cycles			
	From 280 to 250 mg/m 		From 250 to 225 mg/m 					
	N	%	N	%				
Adverse Event								
Other								

Listing of the reasons for vinflunine dose reduction in arm A.

### 9.2.5.2. **Methotrexate dose reductions**

Number of patients with at least one dose reduction of methotrexate:

Number of cycles with at least dose reduction of methotrexate:

Number of administrations with a dose reduction of methotrexate:

Reasons for methotrexate dose reductions (as per protocol) in arm A:

Reason for dose reduction	Dose reduction as per protocol (from X to Y) in mg/m 			N cycles	
	30	30			
	20	<20			
N(%)	N(%)	N(%)	N(%)		
Adverse Event					
Other					

Reasons for methotrexate dose reductions (as per protocol) in arm B:

Reason for dose reduction	Dose reduction as per protocol (from X to Y) in mg/m 						N cycles
	40	40	40	30	30	20	
	30	20	<20	20	<20	<20	
N(%)	N(%)	N(%)	N(%)	N(%)	N(%)	N(%)	N(%)
Adverse Event							
Other							

Listing of the reasons for methotrexate dose reductions,

The format of the tables may be slightly modified according to observed data.

### 9.2.6. **Treatment cancellation**

Cancellation of day 1 vinflunine administration is not allowed by the protocol. Methotrexate dosing may be cancelled in both arms (D8 in Arm A and D8/D15 in Arm B) as per protocol (§ 5.2.3 and § 5.2.4 of the protocol).

The number of cycles with at least one day of methotrexate cancelled and number of patients with at least one day of dosing cancelled will be displayed. Reasons for treatment cancellation will be provided.

Number of patients with at least one methotrexate dose cancelled,

Number of cycles with at least one methotrexate dose cancelled,

- Reasons for methotrexate on D1 / D8 / D15 dose cancellation, per patient and per cycle,
- Listing of methotrexate dose cancelled and reason,

If cancellation are observed for Vinflunine, they will be described in the same way as for Methotrexate.

### **9.2.7. Dose interruption**

For both arms, the number of patients and cycles with an infusion interruption will be presented as well as the reasons.

- Number of patients with at least one infusion interruption,
- Number of cycles with at least one infusion interruption,
- Reasons for infusion interruption,
- Listing of the reasons for infusion interruption,

### **9.2.8. Treatment delay**

The number of patients and cycles delayed will be presented with reasons for treatment delay.

A treatment cycle will be considered as delayed if administered  $\geq 4$  days after the planned date with a three weeks interval from day 1 of previous cycle.

The delays will be categorized as follows:

- [4 – 7 days],
- [7 – 14 days],
- 14 days.

The following information will be described:

- Number of patients with at least one cycle delayed by four days or more, by arm
- Number of cycles delayed, by arm
- Categorized groups of cycle delay, by arm
- Reasons for cycle delay of four days or more, by arm
- Listing of the cycles delayed with reasons,

### **9.2.9. Dose discontinuations**

Patients in arm A who require discontinuation of methotrexate may remain on vinflunine alone for the remainder of the study. Likewise, patients who require discontinuation of vinflunine may remain on methotrexate alone for the remainder of the study.

The following information will be provided for patients treated in arm A:

- Number of patients and cycles with discontinuation of vinflunine or methotrexate (arm A),

Number of cycles, cumulative dose (by patient), dose intensity (by patient) and relative dose intensity (by patient) of vinflunine / methotrexate given in monotherapy,

Listing of patients with discontinuation of vinflunine or methotrexate with drug administration for cycles given in monotherapy (arm A),

### 9.2.10. Route of administration and setting

The route of vinflunine and methotrexate administration and setting will be presented by patient and by cycle.

Route of administration and setting by patient and by treatment arm:

Route of administration	Arm A		Arm B	
	N	%	N	%
Central venous line				
Peripheral vein				
Change in route of administration				
No				
Yes				
Setting				
Out-patient clinic				
In-patient clinic				
Change in setting				
No				
Yes				
Number of patients				

Route of administration by cycle:

Courses	Arm A		Arm B	
	Central venous line N (%)	Peripheral vein N (%)	Central venous line N (%)	Peripheral vein N (%)
1				
2				
3				
4				
5				
6				
...				
Number of cycles				

Route of administration by administration (Methotrexate only)

Courses	Arm A		Arm B	
	Central venous line N (%)	Peripheral vein N (%)	Central venous line N (%)	Peripheral vein N (%)
Number of administrations of MTX				

### 9.2.11. Concomitant medications

Medications administered concomitantly with the study treatment will be summarized according to the prophylactic indication, tumour related indication, adverse event indication, pre-treatment events indication, medical history indication and whatever the intent, by patient and by cycle.

## 10. EFFICACY ANALYSES

### 10.1. PRIMARY EFFICACY ANALYSIS

The final analysis of overall survival was planned to be conducted once the required number of events (437 deaths) has been observed. The statistical analysis will actually be conducted on the 459 randomised patients.

**The primary efficacy population will be the intent-to-treat (ITT) population.**

The hypothesis of superiority in terms of OS of vinflunine in combination with methotrexate versus methotrexate alone will be accepted if the p-value from a stratified log-rank test is smaller than 0.05.

The stratification factors will be:

- WHO performance status (0 vs 1),
- Refractory or resistant to platinum versus other,
- Prior radiotherapy (yes versus no),
- Prior treatment with any anti-EGFR medication (yes versus no)

Centre will not be used for the analysis because of the high number of participating centres.

The stratified log-rank test, hazard ratio and 95% confidence interval of the hazard ratio will be computed using the SAS® procedure «PHREG». The treatment arm will be entered as a covariate in the Cox proportional hazard model and the variables of stratification at randomisation (except centre) will be entered as stratification factors in the model.

### 10.2. SUPPORTIVE ANALYSIS OF THE PRIMARY EFFICACY PARAMETER

According to the protocol amendment 11, no supportive analysis of the primary efficacy parameter will be performed.

### 10.3. SENSITIVITY ANALYSES OF THE PRIMARY EFFICACY PARAMETER

According to the protocol amendment 11, no sensitive analysis of the primary efficacy parameter will be performed.

## 10.4. SECONDARY EFFICACY ANALYSES

### 10.4.1. Progression Free Survival

The analysis of Progression Free Survival (PFS) will be conducted in the ITT population.

#### ***10.4.1.1. Primary analysis of PFS***

The primary analysis of PFS will be done in the ITT. The stratified log-rank test, hazard ratio and 95% confidence interval of the hazard ratio will be computed using the SAS® procedure «PHREG». The treatment arm will be entered as a covariate in the Cox proportional hazard model and the variables of stratification at randomisation (except centre) will be entered as stratification factors in the model.

### 10.4.2. Tumour response

The analyses of tumour response will be performed in the ITT population.

#### ***10.4.2.1. Objective response rate and disease control rate***

Objective Response Rate (ORR) and Disease Control Rate (DCR) in each treatment arm will be estimated and presented along with a corresponding 95% confidence interval. The ORR and DCR will be compared between the two arms with a Cochran-Mantel-Haenszel (CMH) test. The stratification factors will be those defined above.

#### ***10.4.2.2. Duration of overall response and disease control***

Duration of response and duration of disease control will be analysed on the ITT population. A stratified log-rank test will be used to compare the two treatment arms. The stratification factors will be those defined above.

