### 3. SAMPLE SIZE

The primary objective of the study was to show that the vinflunine plus methotrexate (arm A) is superior to methotrexate alone (arm B) in terms of overall survival. The final analysis will require at least 437 deaths; this is the number of events needed for a two sided, log-rank test at an alpha = 0.05 significance level to have 90% power to show a statistically significant difference when the true hazard ratio is 0.733 (i.e., when the median OS in the vinflunine arm is 7.5 months and the median OS in the control arm is 5.5 months). An expected total number of 530 patients was planned. It was estimated that the study will take approximately 19 months to accrue and the OS analysis is expected to be performed ten months following the last patient accrued. The anticipated lost to follow-up is estimated to be 5%.

Following the decision to stop the recruitment:

- The statistical analysis will actually be conducted on the 459 randomised patients.
- 325 events should be observed at the end of study allowing a power of 80%.

Whatever the number of events at the end of study, the final analysis of OS (primary analysis) will be performed on the ITT population. Only descriptive analyses will be performed on all secondary efficacy analyses for ITT population.

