### 4.2.1. Progression free survival

Progression-free survival will be calculated from the date of randomisation until the date of progression or death (whatever the reason of death). Patients lost to follow-up, or without a known record of progression or death at time of analysis will have the progression-free survival censored at the date of last tumour assessment or the date of last contact of a follow-up showing no progression, whichever occurs last.

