#### **4.2.4. Duration of response**

The duration of objective response will be measured for responders (CR + PR) from the time that measurement criteria are first met for complete or partial response (whichever status is recorded first), until the first date that recurrent or progressive disease is objectively documented or the date of death due to any cause. The duration of response of patients who are lost to follow-up or reach the time point of analysis without a known record of progression or death will have the duration of response censored at the date of last tumour assessment or last contact date of a follow-up showing no progression, whichever occurred last. For patients who receive a new anti-cancer treatment in the absence of progression, the duration of overall response will be censored at the date of first administration of the new anti-cancer treatment.

Following the protocol amendment 11, the number of censored patient will be higher than expected. The result should be interpreted with cautiously.

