#### **4.2.5. Duration of disease control**

The duration of disease control will be measured for patients with objective response or stable disease, from the date of randomisation until the date of progression or the date of death whatever the cause. The duration of disease control of patients who are lost to follow-up or reach the time point of analysis without a known record of progression or death will have the duration of disease control censored at the date of last tumour assessment or last contact date of a follow-up showing no progression, whichever occurred last. For patients who received a new anti-cancer treatment in the absence of progression, the duration of disease control will be censored at the date of first administration of this new anti-cancer treatment.

Following the protocol amendment 11, the number of censored patient will be higher than expected. The result should be interpreted with cautiously.

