## 8. STATISTICAL METHODS

### 8.1. STATISTICAL SOFTWARE AND METHODOLOGY

The statistical analysis will be performed by Institut de Recherche Pierre Fabre. Data will be analysed using the SAS® system software version 9.4 (or later if available) for Windows®. All statistical tests will be two-sided at a 5% level of significance unless otherwise specified.

Summary tables will be provided according to the standard format of Institut de Recherche Pierre Fabre developed for the vinflunine chemotherapy.

All descriptive statistics will be presented in summary tables by treatment arm.

Continuous data will be summarized with the following items: frequency, median (if  $n > 3$ ), range and mean and standard deviation if relevant.

Categorical data will be presented in contingency tables with frequencies and percentages of each modality (including missing data modality).

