## 8.5. STATISTICAL METHODS FOR TIME DEPENDENT DATA

To describe time dependent parameters, Kaplan-Meier curves and life tables by treatment arm will be provided. Confidence intervals on the median will be calculated using the Brookmeyer and Crowley method. Hazard ratio and 95% confidence intervals will be reported. A stratified Cox proportional model will be performed to compare the two treatment arms taking into account the stratification factors (except center) used at the time of randomisation.

According to the protocol amendment 11, no multivariate analysis will be performed.

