12.2.2.4	Worst CTCAE grade of SGPT/ALT by patient according to the presence of liver metastases at baseline [Safety set]	12_2_2_4_2e.RTF
12.2.2.4	Worst CTCAE grade of alkaline phosphatase by patient according to the presence of liver and/or bone metastases at baseline [Safety set]	12_2_2_4_2f.RTF
12.3.1.1	Summary of deaths [Safety set]	12_3_1_1a.RTF
12.3.1.1	Listing of dead patients within 30 days after last administration, reason of death, relationship to treatment [Safety set]	12_3_1_1b.RTF
12.3.1.1	Listing of dead patients within 30 days more than 30 days after last administration, reason of death, relationship to treatment [Safety set]	12_3_1_1c.RTF
12.3.1.2	Listing of Serious Adverse Events [Safety set]	12_3_1_2.RTF
14.1.1	Prior medications whatever the indication per patient at baseline [ITT]	14_1_1.RTF
14.1.2	Prior medications with a tumour related indication per patient at baseline [ITT]	14_1_2.RTF
14.1.3	Prior medications with a prophylactic indication per patient at baseline [ITT]	14_1_3.RTF
14.1.4	Prior medications with pre-treatment event indication per patient at baseline [ITT]	14_1_4.RTF
14.1.5	Prior medications with medical history indication per patient at baseline [ITT]	14_1_5.RTF
14.1.6	Prior medical history by patient according to MedDRA System Organ Class and Preferred Term [ITT]	14_1_6.RTF
14.1.7	Pre-treatment events by patient according to MedDRA System Organ Class and Preferred Term [ITT]	14_1_7.RTF
14.2	Progression-Free Survival (PFS-months) [ITT]	14_2_1.RTF
14.2	Progression-Free Survival (PFS-months) [ITT]	14_2_1 FIG.RTF
14.2	Objective Response Rate (ORR) [ITT]	14_2_2.RTF
14.2	Disease Control Rate (DCR) [ITT]	14_2_3.RTF

SECTION	TITLE	RTF reference
14.2	Duration Of Response (months) [ITT]	14_2_4.RTF
14.2	Duration Of Response (months) [ITT]	14_2_4 FIG.RTF
14.2	Duration of Disease Control (months) [ITT]	14_2_5.RTF
14.2	Duration of Disease Control (months) [ITT]	14_2_5 FIG.RTF
14.2	Time to Treatment Failure (months) [ITT]	14_2_6.RTF
14.2	Time to Treatment Failure (months) [ITT]	14_2_6 FIG.RTF
14.2	Time to First Response (months) [ITT]	14_2_7.RTF
14.2	Time to First Response (months) [ITT]	14_2_7 FIG.RTF
14.3	Electrocardiogram: listing of abnormalities at baseline [Safety Set]	14_3_1.RTF
14.3	Electrocardiogram: listing of abnormalities during treatment period [Safety Set]	14_3_2.RTF
14.4.1a	Concomitant medications whatever the indication per patient [ITT]	14_4_1a.RTF

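### The planned log-rank tests of response duration and disease-control duration compare subsets selected after randomisation, despite the ITT label, and contradict the plan's own descriptive-only rule

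*SAP*

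**What the plan says.** SAP 10.4.2.2: "Duration of response and duration of disease control will be analysed on the ITT population. A stratified log-rank test will be used to compare" the arms. The protocol orders the same stratified test in the synopsis (Statistical methods, continued) and in 11.5.3.2.4.3. The latter repeats it in patients with measurable disease. SAP 8.1 sets the level: "All statistical tests will be two-sided at a 5% level of significance unless otherwise specified".

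The definitions are narrower than the population label:

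- SAP 4.2.4: "The duration of objective response will be measured for responders (CR + PR"), with the clock starting at response.
- SAP 4.2.5: "The duration of disease control will be measured for patients with objective response or stable disease, from the date of randomisation".
- Protocol 11.4 restricts both durations in the same way.

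SAP Appendix 1 nevertheless tags the outputs as ITT, for example "Duration of Disease Control (months) [ITT"].

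SAP section 3 also states: "Only descriptive analyses will be performed on all secondary efficacy analyses for ITT population". The protocol synopsis repeats this. So does protocol 11.5.1, which adds a bracketed list naming secondary parameters. SAP 4.2 lists both durations among the secondary parameters.

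SAP 10.4.2.3 and 10.4.2.4 plan no formal comparison for time to first response or time to treatment failure. But SAP 8.5, under time-dependent data in general, says "A stratified Cox proportional model will be performed to compare the two treatment arms", and protocol 11.5.1.2 says the same.

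**The concern.** Randomisation balances the 230 and 229 patients randomised. It does not balance those who later respond or reach disease control. If one arm brings more patients to disease control, its controlled group will tend to include patients of poorer prognosis whom the other arm would have lost before the first assessment. Durations can then differ between arms although treatment changes nothing afterwards.

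The second problem is status. One part of the plan makes these analyses descriptive and another orders a test at 5%. The report could present a p-value as either. The log-rank test of PFS (SAP 10.4.1.1) and the CMH tests of ORR and DCR (SAP 10.4.2.1) collide with the same rule, but they use all randomised patients and have no selection problem.

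**Working it through.** **1. The plan's own figures.** The durations have no stated sample size or power; the only design figures are for OS. Events = 4(1.960 + 1.282)² / (ln(5.5/7.5))² = 437, as stated. Power with 325 events = Φ(½√325 × 0.310 − 1.960) = 79.8%, against the stated 80%. Nothing below changes these.

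**2. Who is compared.** A patient without response has no duration of response. A patient without CR, PR or SD has no duration of disease control. No rule gives such patients a value of zero. ITT can therefore mean only that the subset is drawn from the ITT set. SAP 4.2.7 and 10.4.2.3 use the label this way for time to first response, which is calculated among responders but described in ITT.

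**3. Overlap with PFS.** SAP 4.2.1: "Progression-free survival will be calculated from the date of randomisation until the date of progression or death (whatever the reason of death"). Disease-control duration has the same start and the same events. The difference in rule is that it also censors at new anti-cancer therapy. The randomised comparison on that clock is already the PFS test.

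**4. Subset sizes from the documents' rates.** Methotrexate rates come from protocol 1.1.1 and its Table 2 (pretreated rows). Combination rates come from the phase I results in protocol 1.2.1.4, over 20 evaluable or 31 enrolled patients.

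- Responders, arm B: 229 × 3.9% = 8.9; 229 × 10.8% = 24.7.
- Responders, arm A: 230 × 3/31 = 22.3; 230 × 15% = 34.5.
- Disease control, arm B: 229 × 41.3% = 94.6; 229 × 48% = 109.9.
- Disease control, arm A: 230 × 11/31 (35.5%) = 81.6; 230 × 55% = 126.5. The exact 95% CI for 11/20 is 32 to 77%.

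Four binary factors give up to 2⁴ = 16 strata.

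**5. Illustration for disease-control duration.** These assumptions are not in the documents: log-normal frailty; an arm-specific hazard to week 6 set to give the control rate; the same hazard in both arms after week 6 (baseline median 2, 3 or 4 months); uniform censoring over 2 to 14 months; stratum prevalences of 60, 70, 85 and 50%; stratified log-rank among controlled patients. Rejection of a nominal 5% test, in %:

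| Control, A v B | SD 0 | SD 0.5 | SD 1.0 |
|---|---|---|---|
| 55 v 55% | 4.6–5.7 | 4.6–5.7 | 4.6–5.7 |
| 55 v 48% | 5.3–5.5 | 5.0–5.5 | 6.1–6.5 (5.1–5.5 against A) |
| 55 v 41.3% | 5.4–5.9 | 6.3–7.0 | 10.7–11.7 (10.3–11.3 against A) |
| 35.5 v 41.3% | – | – | 5.6 (4.5 favouring A) |
| 35.5 v 48% | – | – | 9.2 and 10.2 (8.6 and 9.8 favouring A) |

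Monte Carlo standard error is about 0.3 to 0.4 points near 5%. The last two rows rest on fewer settings (one run, then two).

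A different mechanism points the same way. Suppose patients controlled in either arm have a 4-month median, and those controlled only because of arm A have a 2-month median. An unstratified test then rejects in 4.9% of trials at 45 v 45% and in 10.8% at 45 v 55%, nearly all against arm A.

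**The case against.** The strongest reply is that little hangs on this. Only OS has an acceptance rule (SAP 10.1), section 3 already calls secondary analyses descriptive, and SAP section 13 describes an abbreviated report. Inflation is clear only under strong heterogeneity, which no passage supports. All of this stands and limits the severity. It does not rescue the tests. If they are descriptive, the log-rank sentence should go, as it does for the two neighbouring endpoints. The SAP's own caution in 4.2.4 and 4.2.5 concerns extra censoring after amendment 11, not selection, and section 13 does not list these tests among the deletions.

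A reader might infer more than the documents support:

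- **That the bias can only hurt vinflunine.** This holds only if arm A controls more patients. With 11 of 31 enrolled instead of 11 of 20 evaluable, set against 41.3 to 48%, the direction reverses.
- **That the error rate reaches about 27 to 32%.** That needs strong heterogeneity and 27% control in arm B. The 27% comes from a best-supportive-care arm in which 78% received methotrexate.
- **That a smallest detectable hazard ratio for response duration can be quoted.** It would apply a large-sample formula to a log-rank variance of only about 2 to 6, with assumed medians, censoring and stratum prevalences. What the documents support is that responders are few.

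**Conclusion.** The point holds on the text alone. The plan orders between-arm tests on groups formed after randomisation, under a label that suggests otherwise, and against its own descriptive-only rule. The p-values would not be valid tests of treatment effect.

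The size is illustrative. There is essentially no inflation with equal control or no heterogeneity, about 0 to 2 points with moderate heterogeneity, and about 10 to 12% with strong heterogeneity at 55 v 41.3%. The error runs against the arm that controls more patients. The response-duration test would be uninformative either way.

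Severity is minor to moderate: secondary endpoints only, with OS alpha and power untouched.

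**What to change.** (a) Replace SAP 10.4.2.2 with:

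> Duration of response will be summarised for responders (CR + PR), and duration of disease control for patients with CR, PR or SD, by arm, with Kaplan-Meier medians and 95% CI. Membership of these subsets is determined after randomisation, so the arms are not randomised groups within them. No between-arm test or hazard ratio will be given.

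Delete the matching log-rank sentences in the protocol synopsis and in 11.5.3.2.4.3, including the measurable-disease repeat.

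(b) In SAP 8.5 and protocol 11.5.1.2, limit the hazard-ratio and Cox sentences to OS and PFS.

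(c) In SAP Appendix 1, relabel tables and figures 14_2_4 and 14_2_5 with the subset actually analysed. Protocol 11.4 asks for confirmed response and the SAP does not. That is a separate discrepancy, but the label should say which applies.

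(d) In SAP section 3, the protocol synopsis and protocol 11.5.1, state that secondary efficacy analyses, including those in the bracketed list in 11.5.1, are descriptive. State also that p-values for PFS, ORR and DCR are nominal, unadjusted for multiplicity and support no efficacy claim. Make the 5% level in SAP 8.1, and the same sentence in protocol 11.5.1, subject to this.

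The cost is wording and table labels. Two between-arm p-values and hazard ratios on non-randomised subsets are lost. The duration estimates, the PFS, ORR and DCR comparisons and the OS test all stay.
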